## Procedures and Data Management

**Staffing and responsibilities.** We will hire and train one full time mentor mother for each study hospital. Each mentor mother will be trained to conduct study procedures specific to the study arm allocation. At all sites, mentor mothers will assess eligibility, conduct informed consent procedures and surveys, and facilitate VL testing at the time of delivery and by 6 months postpartum if not retested prior. At sites implementing HITSystem 2.1, mentor mothers will be the primary persons to enter and routinely update patient data. Mentor mothers also will lead patient outreach and follow-up efforts (phone or texting via HITSystem 2.1) and coordinate with community health workers (CHW) for targeted physical tracking if needed for VL testing at research-specific time points. Site Coordinators will routinely visit each study hospital to provide supportive supervision to ensure adherence to study protocols.

**Description of procedure and data collection:** At sites implementing HITSystem 2.1, all patient-specific data including: infant and maternal demographics; women's phone number and patient tracing information; women's appointment attendance and ART medication refills/pill counts; infant's date of birth, birth weight, and gestational age at delivery; dates of maternal VL sample collection, test processing, results return, and notification; and maternal VL results will be entered directly into HITSystem 2.1. ART adherence will be measured by pill counts collected at each consultation via HITSystem 2.1. At SOC sites, all clinical and PMTCT service related data will be collected in the existing paper-based registries by health care providers as part of routine services. Because routine pill counts for ART adherence are well outside of SOC practice and could modify behaviors in the control arm, we will rely on pharmacy refill records and chart review for any provider notes related to adherence. During their monthly site visits, site coordinators will review hospital registries at SOC sites to document patients' PMTCT engagement in study logs.

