**Effectiveness:** Objectives 1 & 2 assessing complete PMTCT retention and viral suppression will evaluate effectiveness. We will also measure adverse outcomes as a result of the program.

**Adoption:** At the *facility-level*, we will note any facilities which decline study participation and reasons for refusal. Among participating hospitals, the facility assessment form – filled out pre-mid-post study implementation – will collect data regarding resource level, patient-provider ratios, annual volume, implementing partners and outside support, and other facility details will be used to assess representativeness with Kenyan health care facilities. At the *provider-level*, adoption will be evaluated through provider surveys, assess the degree to which providers used HITSystem 2.1, determine which components were most beneficial, and assess facilitators and barriers to HITSystem 2.1 adoption. *Patient surveys* will similarly assess utility of SMS outreach components and suggestions to optimize benefit.

**Implementation:** Any changes to HITSystem 2.1 programming or study protocols will documented in research logs and/or through IRB amendments. Any changes to HITSystem 2.1 implementation at the hospital-level (i.e. location changes of desktop to better suit workflow, changes in key users, etc) will also be documented in study logs to guide implementation recommendations. We will review all HITSystem texting logs during the implementation period to assess fidelity of the SMS component by calculating the proportion of SMS sent according to participant preference (correct frequency and content) and the proportion received by a functioning mobile number. We will compare this with participants' reports of the number of SMS received as part of the study and the reasons for these SMS, which will be collected as part of the patient surveys.

**Maintenance:** Continued HITSystem 2.1 enrollment after the study enrollment period has ended (years 3-5) and utilization after the study follow up period (year 4-5) will serve as an indicator of system maintenance. In Years 3-5, the US-based study manager will compare the overall number of HITSystem 2.1 enrolments with PMTCT registers to assess if reach is being maintained. Using the HITSystem 2.1-generated alerts report, s/he will document the number and duration of provider alerts as a measure of system use.

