**Table 7. RE-AIM guided implementation evaluation**

|                       | Measures  | Data sources  |
|-----------------------|---|---|
| Reach          | 
 
•HITS 2.1 enrollment vs refusal
 
•Patient characteristics
 
                 | 
 
•HITS 2.1 vs. hospital registers
 
•Patient surveys
 
                              |
| Effectiveness  | 
 
•Aim 1 & Aim 2 primary outcomes
 
   | 
 
•HITS 2.1
 
•Hospital registers
 
  |
| Adoption       | 
 
•Provider & hospital details
 
•System use
 
•Component benefit
 
 | 
 
•Facility assessment forms
 
•Provider surveys
 
•Patient surveys
 
         |
| Implementation | 
 
•Changes to HITS 2.1 or implementation
 
•SMS delivery/receipt
 
             | 
 
•IRB amend/ field notes/study logs
 
•HITS 2.1 SMS log
 
•Patient surveys
 
 |
| Maintenance    | 
 
•HITS 2.1 enrollment and alert tracking: Y4-5
 
•Cost-effectiveness
 
        | 
 
•HITS 2.1 vs hospital registers
 
•HITS 2.1 alerts
 
•Aim 3 analyses
 
      |

[i.e., strikes, reagent stock outs, laboratory machine breakdowns], email exchanges with other relevant summary documentation regarding implementation, meeting minutes of team calls) will be reviewed and coded in summary themes relevant to the implementation process and experience, per the RE-AIM model. These qualitative data will augment the quantitative survey data from provider and patient interviews.

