## 11.0 Budget

Please note, all budgetary information is subject to change based on final staffing decisions and final award amount. All amounts are shown in U.S. dollars (USD, \$)

Below the combined estimated study budget for years 1 through 5 and total across all five years are outlined. These funds will be distributed among the four partnering institutions (KUMC, GHI, KEMRI, CMH).

| Overview                                       | 01 Year        | 02 Year        | 03 Year        | 04 Year        | 05 Year        | 01-05 Years      |
|--|----------------|----------------|----------------|----------------|----------------|------------------|
| Salaries                                       | 268,822        | 270,424        | 275,831        | 281,351        | 266,898        | 1,363,326        |
| Fringes  | 86,094         | 82,836         | 84,489         | 86,182         | 83,376         | 422,977          |
| Consultants                                    | 12,000         | 2,500          | 2,000          | 1,500          | 6,500          | 24,500           |
| Equipment                                      | 0              | 0              | 0              | 0              | 0              | 0                |
| Materials and Supplies                         |                |                |                |                |                |                  |
| Training                                       | 8,300          | 0              | 0              | 0              | 0              | 8,300            |
| Printing                                       | 1,100          | 2,900          | 3,000          | 3,000          | 2,900          | 12,900           |
| Communication                                  | 5,200          | 10,200         | 10,200         | 10,200         | 10,100         | 45,900           |
| HITSsystem usage costs (licensing/airtime)     | 7,800          | 9,000          | 9,000          | 9,000          | 9,000          | 43,800           |
| Staff support (MM salary, SC health insurance) | 36,720         | 69,840         | 69,840         | 69,840         | 36,720         | 282,960          |
| VL testing costs                               | 15,720         | 14,690         | 10,190         | 1,440          | 0              | 42,040           |
| Patient tracing                                | 4,320          | 8,640          | 8,640          | 6,480          | 0              | 28,080           |

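### Maintenance is defined by calendar years in which the study still budgets for mentor mothers and licences, so the indicator cannot separate sustained facility use from study-supported operation

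*Combined protocol and SAP*

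**What the plan says.** The Maintenance paragraph (Objective 3 specific methods) uses two measures. For reach, in years 3-5 the study manager will "compare the overall number of HITSystem 2.1 enrolments with PMTCT registers to assess if reach is being maintained". For use, the study manager will "document the number and duration of provider alerts as a measure of system use"; the paragraph states that "utilization after the study follow up period (year 4-5) will serve as an indicator of system maintenance". Table 7 gives a single window for both: "HITS 2.1 enrollment and alert tracking: Y4-5".

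Under Procedures and Data Management, the study employs a full-time mentor mother at every study hospital, and at HITSystem sites "mentor mothers will be the primary persons to enter and routinely update patient data". Monthly supportive supervision, including technical help and retraining, has no stated end.

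In section 11.0, two lines pay for operation: "Staff support (MM salary, SC health insurance") and "HITSsystem usage costs (licensing/airtime"). Both have an amount in all five years. The section warns that budget figures may change. Section 9.0 says that sustainability plans will be worked out with the counties, but no part of the protocol gives a date, a staff transfer or a payer for the period after study support.

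**The concern.** Objective 3 is meant to inform lasting use of HITSystem in government facilities. Both maintenance measures come from work that the protocol assigns mainly to study-hired staff: enrolling women in the system, and entering the data that raise and clear alerts. The window begins when data collection on participants stops. That is a different event from the study withdrawing its staff and payments.

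If the mentor mothers keep their HITSystem duties into years 4 and 5, enrolment could match the registers and alerts could be resolved promptly with little use by facility employees. Equally good figures could come from facilities that have adopted the system. The planned report would look the same in both cases, so a favourable result could not be read as maintenance in the sense that Objective 3 intends.

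**Working it through.** **1. Reproducing the budget lines (section 11.0, USD).**

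| Line | Y1 | Y2 | Y3 | Y4 | Y5 | Sum | Stated total |
|---|---|---|---|---|---|---|---|
| Staff support | 36,720 | 69,840 | 69,840 | 69,840 | 36,720 | 282,960 | 282,960 |
| Licensing/airtime | 7,800 | 9,000 | 9,000 | 9,000 | 9,000 | 43,800 | 43,800 |

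Both totals agree.

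**2. Amounts inside the maintenance windows.**
- Years 3-5: staff support 69,840 + 69,840 + 36,720 = 176,400; licences 3 × 9,000 = 27,000; together 203,400.
- Years 4-5: staff support 69,840 + 36,720 = 106,560; licences 2 × 9,000 = 18,000; together 124,560.
- Year 5 against year 4: staff support 36,720/69,840 = 53%; licences 9,000/9,000 = 100%.

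Neither line is zero in any maintenance year. The staff line covers all 12 hospitals and includes health insurance, so these sums are not intervention-site mentor-mother pay alone.

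**3. Where the window falls (section 7.0).** Start-up takes 6-8 months, accrual 18 and follow-up 12. Enrolment ends at month 6 + 18 = 24 to 8 + 18 = 26. Follow-up ends at month 24 + 12 = 36 to 26 + 12 = 38. This matches the years in the Maintenance paragraph on the original timeline.

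**4. What the year-5 staff sum can mean.** Assume that the line is a fixed insurance amount c plus a full-year salary total M for 12 mentor mothers, and that year 5 holds half of M:
- c + M = 69,840 and c + M/2 = 36,720.
- M = 2 × (69,840 − 36,720) = 66,240, or 66,240/12 = 5,520 per mentor mother per year; c = 3,600.
- Year-5 salary = 33,120, which is 12 people for half a year (12 × 2,760) or six for a full year (6 × 5,520).

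Year 1 carries the same sum, and its first 6-8 months are start-up. That makes the half-year reading plausible but does not confirm it. Under it, intervention sites would have about 6 months of year 5 without mentor-mother pay. Under the six-person reading they would have none if the six are at intervention sites, and 12 if the six are at control sites. The documents do not say which applies.

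**5. Factors that move the window.** Section 7.0 extends enrolment and shortens maintenance monitoring at slow sites. The sample-size text for Objective 2 adds 300 women across ten sites, which may delay the end of enrolment there. Neither creates a period free of study funding.

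**The case against.** The strongest reply is that the documents do not show that the study still runs the system in years 4 and 5. The Maintenance paragraph offers an indicator, and enrolment after study accrual has closed does carry information on routine use. The staffing text does not say whether mentor mothers keep their HITSystem duties after follow-up, and the budget line is pooled and provisional. A reader might infer that the figures show study-funded operation rather than sustained use. The documents support only that the two cannot be separated.

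A reader might also put a number on it. If all 12 mentor mothers are paid to month 54, the study-staffed share of the post-follow-up period is (54 − 38)/(60 − 38) = 73% to (54 − 36)/(60 − 36) = 75%. That needs the half-year reading and the original timeline. If follow-up ended at month 44, as an illustration, the share would be (54 − 44)/(60 − 44) = 63%. No such percentage should be relied on.

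External support is also partly the delivery model. The protocol likens its monthly visits to programmatic support for HITSystem 1.0, and Objective 4 counts licensing and implementation support as intervention costs. A study-paid licence is therefore something to disclose; it does not show that facilities are not using the system.

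Other data help in part. The end-of-study provider survey records role, hours and days of use, and reasons for logging in. Study logs record changes in key users, and the facility form records outside support. But the survey is self-report from about five providers per site and can include mentor mothers, and none of these sources is linked to the maintenance measure or to the end of support.

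Finally, Objective 3 is unpowered and descriptive, and the protocol ties roll-out to efficacy and cost-effectiveness. It does not say that the maintenance result would drive that decision. These points limit the finding, but they do not repair the definition.

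**Conclusion.** The concern holds in this form: the maintenance window is set by calendar, study-hired mentor mothers are the primary data-enterers, and the budget funds the line that includes their salary, and the licences, in every year of the window with no handover stated. The measures therefore cannot show use sustained without study funding. They do not show its absence either.

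In size, USD 203,400 of these two lines falls in years 3-5 and USD 124,560 in years 4-5, taking the provisional budget as printed. The length of any period without study-paid staff at intervention sites is not determinable. Licences are budgeted at the full rate to the end of year 5 under every reading. The text and Table 7 also disagree on the enrolment window (years 3-5 against years 4-5).

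The change is worth making because it alters what the maintenance result can conclude. It concerns a descriptive implementation outcome and affects neither primary outcome.

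**What to change.** In the Maintenance paragraph and Table 7:

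- Record, for each intervention site, the date on which study-paid mentor-mother HITSystem duties end.
- Report HITSystem enrolments divided by register enrolments, and alert number and duration, separately before that date (*continued use with study support*) and after it (*maintenance*).
- Where a site has no period after that date, state that maintenance was not assessable there.
- State that licences and airtime remained study-funded, if that is what happened.
- Split entries by user role only if the system logs allow it. The protocol describes password access but no user-level record of entries. Otherwise, report the end-of-study provider survey by role, with the log of changes in key users.
- Give the same years in the text and in Table 7.

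The enrolment and alert reports are already planned, so the main cost is wording, one date per site and a split of existing output. The role split may need extra work or prove impossible. The downside is that the unsupported window may be short or empty, so the maintenance estimate will be less precise and probably less favourable.

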**Table 7. RE-AIM guided implementation evaluation**

|                       | Measures  | Data sources  |
|-----------------------|---|---|
| Reach          | 
 
•HITS 2.1 enrollment vs refusal
 
•Patient characteristics
 
                 | 
 
•HITS 2.1 vs. hospital registers
 
•Patient surveys
 
                              |
| Effectiveness  | 
 
•Aim 1 & Aim 2 primary outcomes
 
   | 
 
•HITS 2.1
 
•Hospital registers
 
  |
| Adoption       | 
 
•Provider & hospital details
 
•System use
 
•Component benefit
 
 | 
 
•Facility assessment forms
 
•Provider surveys
 
•Patient surveys
 
         |
| Implementation | 
 
•Changes to HITS 2.1 or implementation
 
•SMS delivery/receipt
 
             | 
 
•IRB amend/ field notes/study logs
 
•HITS 2.1 SMS log
 
•Patient surveys
 
 |
| Maintenance    | 
 
•HITS 2.1 enrollment and alert tracking: Y4-5
 
•Cost-effectiveness
 
        | 
 
•HITS 2.1 vs hospital registers
 
•HITS 2.1 alerts
 
•Aim 3 analyses
 
      |

[i.e., strikes, reagent stock outs, laboratory machine breakdowns], email exchanges with other relevant summary documentation regarding implementation, meeting minutes of team calls) will be reviewed and coded in summary themes relevant to the implementation process and experience, per the RE-AIM model. These qualitative data will augment the quantitative survey data from provider and patient interviews.

#### Objective 4 specific methods

Evaluate the costs and cost-effectiveness of HITSystem 2.1 for increasing: 1) complete PMTCT retention, 2) viral suppression, and 3) modeled estimates for pediatric HIV infections averted

We will establish a unit associated with each type of resource used, estimate the dollar value of each resource, calculate the number of units used, and multiply the units of resources used by the dollar cost for each. Costs (licensing, computing/telecommunication, and personnel/training) will then be summed to derive the low, medium, and high estimates of the total cost of the intervention. Research (research personnel, remuneration) costs will be calculated separately. We will then remove the costs saved with HITSystem 2.1 from the gross program cost. We will conduct sensitivity analyses with a range of estimates for HIV prevalence, rates of viral suppression, mother-to-child transmission rates, and patient volume to assess variations in cost effectiveness outcomes driven by key epidemiologic or demographic data.

The primary driver of the proposed cost-effectiveness analyses for HITSystem 2.1 will be the estimated reduction in the proportion of infants diagnosed with HIV at the initial test at 6-weeks of age. Since maternal nonadherence to ART, long turn-around time for VL results, and failure to take clinical action based on detectable VL results represent wasted investments in PMTCT services, secondary drivers of the cost-effectiveness analyses will be the proportion of (1) women with optimal ART adherence during the antenatal and post-partum periods, (2) women with VL results returned in time for prompt clinical action (by 36 weeks gestation) and (3) detectable VL results that trigger guideline-adherent clinical action.

We will use the number of perinatal transmissions observed in the study (intervention v control), but since the actual numbers are expected to be low, we will also rely on viral suppression data to estimate transmission on a larger scale. Based on literature assessments of maternal viral load and perinatal HIV transmission of HIV, we will estimate rates of transmission at 2.5% and 22.5% for virally suppressed and unsuppressed women, respectively. We will use the estimated number of transmissions in intervention and control sites to compute savings from pediatric infections averted (lifetime ART costs for infants, HIV-related mortality). Data collected on ART adherence and VL testing will be used to calculate the wastage saved by HITSystem 2.1. VL test costing data have been assessed at the national level, and costing estimates for maternal and pediatric ART are available by regimen, but outcome data from the proposed study are needed to adequately calculate the benefits of HITSystem 2.1. Anticipated costs, costs savings, and benefits are outlined below, Table 8.

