**Table 8. Anticipated costs, savings and benefits for cost-effectiveness analysis**

| HITSystem 2.0 Intervention Costs  | Anticipated Cost Savings   | Anticipated Benefits                         |
|---|--|--|
| training, licensing, internet, computer/modem, implementation support
*costs to health system may increase with higher rates of VL testing | Reduced: delayed/un-returned VL results, detectable VL results w/out clinical action, poor maternal ART adherence, pediatric infections and associated costs | QALY saved (infants)
QALY saved (mothers) |

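### The Objective 4 costing rule nets off downstream savings but has no step that adds the cost of the extra viral load tests and follow-on services

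*Combined protocol and SAP*

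**What the plan says.** The costing rule is in the protocol, Objective 4 specific methods. It opens generally: the team will "establish a unit associated with each type of resource used, estimate the dollar value of each resource", count units and multiply. The next sentence names what is added up: "Costs (licensing, computing/telecommunication, and personnel/training) will then be summed", giving a low, a medium and a high total for the intervention. Research personnel and remuneration are costed separately. Then comes the subtraction: "We will then remove the costs saved with HITSystem 2.1 from the gross program cost".

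Robustness is addressed by "sensitivity analyses with a range of estimates for HIV prevalence, rates of viral suppression, mother-to-child transmission rates, and patient volume".

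On unit costs, the section says that "VL test costing data have been assessed at the national level" and that maternal and paediatric ART costs can be had by regimen. The trial data on these services are given one stated use: "Data collected on ART adherence and VL testing will be used to calculate the wastage saved by HITSystem 2.1".

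Table 8 lists training, licensing, connectivity, hardware and implementation support as intervention costs, with a starred note in the same column: "costs to health system may increase with higher rates of VL testing". Its savings column includes fewer late or unreturned VL results, fewer detectable results left without action, better maternal adherence and fewer paediatric infections.

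**The concern.** HITSystem 2.1 is meant to make more services happen. VL testing, clinical action after a detectable result and infant-diagnosis linkage are components of the Objective 1 primary outcome (Table 6). Such services use resources. The rule lets their benefits in, as savings, but names no step at which their cost enters. Table 8 counts fewer unaddressed detectable results as a saving, yet the counselling or regimen change that addresses them is not a cost item anywhere.

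If the rule is followed literally, net cost is too low by the value of the added services, and so is any cost per woman retained, per woman suppressed or per infection averted. That is the direction of the Objective 4 hypothesis. Two analysts working from this text could also reach different net costs, depending on how much weight each gives to the Table 8 note.

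**Working it through.** The documents state no net cost or cost-effectiveness ratio, so there is no figure to reproduce. The check is of the formula, followed by an illustration of scale.

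**1. Formula.** Let P be the three summed programme categories, S the savings, and D the sum over services of (between-arm difference in volume × unit cost).
- As written: net cost = P − S.
- With service costs: net cost = P + D − S.
- The difference is D. The written rule understates net cost if D is positive and overstates it if D is negative.

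**2. Where each item appears.**

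| Item | Summed cost | Table 8 cost column | Sensitivity analyses |
|---|---|---|---|
| Extra routine VL tests | no | starred note, unquantified | no |
| Counselling, regimen change | no | no | no |
| Infant tests | no | no | no |

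**3. Illustrative size of D for VL tests.** Inputs:
- Intervention women: 6 clusters × 96 = 576 (Sampling).
- Expected rise in guideline-adherent testing: 20 percentage points (Sampling; Table 3).
- Extra tests per additional adherent woman: 1 or 2 (assumption).
- Cost per test: USD 10 to 40 (assumption; the documents give none).

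Extra tests: 576 × 0.20 × 1 = 115; 576 × 0.20 × 2 = 230.

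Cost: 115.2 × 10 = USD 1,152; 230.4 × 40 = USD 9,216.

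The enlarged sample (30 more women at each of ten sites) gives 696 to 756 intervention women, depending on the arms of the two closed sites. The cost is then USD 1,392 (696 × 0.20 × 10) to USD 12,096 (756 × 0.40 × 40).

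A wider case raises pilot coverage (49.8% in pregnancy, 21.7% postpartum; Introduction) to 100% for one test per period: 576 × (0.502 + 0.783) = 740 tests, or about USD 7,400 to 29,600.

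**4. Scale against the five-year budget (section 11.0).**
- Licensing and airtime only, USD 43,800: 3% to 21%; wider case 17% to 68%.
- Adding training (8,300) and, by assumption, half of the staff-support line for 6 of 12 sites (282,960 / 2 = 141,480): USD 193,580. The shares become 0.6% to 4.8%; wider case 3.8% to 15.3%.

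**5. Per infection averted, at the plan's own rates.** Detectable VL is 35% versus 11%; transmission is 22.5% unsuppressed and 2.5% suppressed.
- Averted per woman: (0.35 − 0.11) × (0.225 − 0.025) = 0.048.
- Added cost per woman at two tests: 0.20 × 2 × USD 10 to 40 = USD 4 to 16, or USD 83 to 333 per infection averted.
- Wider case: 1.285 × USD 10 to 40 = USD 12.85 to 51.40, or USD 268 to 1,071.

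**6. Sign for follow-on care.** The pilot found documented action for 28.9% of patients with detectable VL. Per 100 women all tested, standard care gives 35 × 0.289 = 10.1 actions and HITSystem gives 11 × (share acted on). HITSystem exceeds standard care only if that share is above 10.1 / 11 = 92%. If only 49.8% of standard-care women are tested and all HITSystem women are, the threshold falls to (10.1 × 0.498) / 11 = 46%. The sign is not fixed in advance.

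**The case against.** A reader might infer that the plan leaves out the cost of extra VL testing altogether. It does not. The Table 8 note already sits in the intervention-cost column, a national VL cost source is cited, and the opening reference to every resource type could be read to include tests. This stands: VL testing is acknowledged. What is missing is a step that brings it into net cost.

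A reader might also infer that the result is shown to be biased. That needs the three-category list to be exhaustive and Table 8 to be ignored, and no ratio or threshold value is given against which to judge the effect.

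Nor do the 20 points mean 200 newly tested women per 1,000. They are women reaching full guideline-adherent testing, and some would already have had one test. The comparison with licensing and airtime alone also flatters the size; against a fuller programme cost the main illustration is below 5%.

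Follow-on care need not cost more, since the plan expects detectable VL to fall. Finally, nothing says that mentor-mother HITSystem time is classed as research: personnel is among the summed intervention costs. The plan only fails to say how that time is divided.

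These points limit the size and certainty of the concern. They do not supply the missing term, and none of them covers the sensitivity analyses.

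**Conclusion.** The concern holds as a gap in the costing rule. Downstream savings enter net cost; the acknowledged VL testing cost is not carried into the sum; follow-on services are not listed as costs; and the sensitivity analyses vary neither the volumes nor the unit costs of these services. For VL tests the risk runs in favour of HITSystem, because the intervention is designed to increase them. For counselling and regimen changes the sign is open.

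The size is unknown. The main illustration of USD 1,150 to 9,200 rests on an assumed unit cost, one or two extra tests per additional adherent woman and 576 women; it bounds nothing. Whether the cost-effectiveness conclusion would change cannot be told, because the documents give neither a lifetime ART cost nor a threshold value. The point should be corrected before the Objective 4 analysis, but it does not touch the two primary outcomes.

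**What to change.** In Objective 4 specific methods, state: net cost = programme cost + sum over services of (between-arm difference in routine VL tests, infant tests, counselling sessions and regimen changes, including their ART cost, × unit cost, whichever sign it takes) − savings. Make the existing Table 8 note a costed line.

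- **Exclude** the research VL test at delivery and the study-initiated 6-month VL and infant PCR tests (Objective 2 specific methods). The study-initiated VL tests go to women without a routine postpartum test, so counting them could hide the increment sought.
- **Vary** service volumes and unit costs in the sensitivity analyses. The volume range should allow for the reagent stockout, in which 198 women and 320 infants missed routine testing.
- **Give sources** for counselling and infant-test unit costs. None is cited for counselling. The title of the national VL costing report (reference 49) also names early infant diagnosis and may serve.
- **Divide mentor-mother time** between HITSystem data entry and outreach (intervention cost) and consent and surveys (research cost), and state the basis.

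The cost is a little more costing work. VL coverage and clinical action are already secondary outcomes, but counselling at control sites depends on chart review and may be under-recorded, which should be stated as a limitation. The ratio may become less favourable to HITSystem.
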